4.0 PATIENT ELIGIBILITY AND INELIGIBILITY

4.1 Conditions for patient eligibility

A patient cannot be considered eligible for this study unless all of the following conditions are met:

- 4.1.1 The patient must have consented to participate and, prior to beginning specific study procedures, must have signed and dated an appropriate IRB-approved consent form that conforms to federal and institutional guidelines for study treatment and for submission of tumor and blood samples as required by FC-9 correlative science studies (see [Section 6.0](#)).
- 4.1.2 Patients must be ≥ 18 years old.
- 4.1.3 The ECOG performance status must be 0 or 1 (see [Appendix A](#)).
- 4.1.4 There must be histologic confirmation of a diagnosis of colorectal adenocarcinoma.
- 4.1.5 The tumor must have been determined to be microsatellite stable (MSS).
- 4.1.6 There must be documentation by PET/CT scan, CT scan, or MRI, that the patient has evidence of measurable metastatic disease per RECIST 1.1.
- 4.1.7 Patients must have an accessible metastatic lesion for pretreatment core biopsy.
- 4.1.8 Unless either drug is medically contraindicated, patients must have received oxaliplatin and irinotecan as part of standard metastatic chemotherapy regimens.
- 4.1.9 The patient must have multiple sites of metastatic disease with at least one lesion amenable to treatment with stereotactic radiation therapy (SBRT) in the lung or liver and at least one lesion not being irradiated and meeting RECIST 1.1. (See [Appendix B](#)).
- 4.1.10 At the time of study entry, blood counts performed within 2 weeks prior to study entry must meet the following criteria:
 - ANC must be $\geq 1500/\text{mm}^3$,
 - Platelet count must be $\geq 100,000/\text{mm}^3$; and
 - Hemoglobin must be ≥ 9 g/dL.
- 4.1.11 The following criteria for evidence of adequate hepatic function performed within 2 weeks prior to study entry must be met:
 - Total bilirubin must be $\leq 1.5 \times \text{ULN}$ (upper limit of normal) for the lab unless the patient has a bilirubin elevation $> 1.5 \times \text{ULN}$ to $3 \times \text{ULN}$ due to Gilbert's disease or similar syndrome involving slow conjugation of bilirubin; *and*
 - AST and ALT must be $\leq 2.5 \times \text{ULN}$ for the lab *with the following exception*: for patients with documented liver metastases, AST and ALT must be $\leq 5 \times \text{ULN}$.

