Gastrointestinal disorders			
Diarrhea/Enterocolitis (See Sections 8.5.1 and 8.5.4 .)	1	Maintain study dose schedule without delay; adjust antidiarrheal medication.	
	2	Hold study therapy and adjust antidiarrheal medication. Once event is stabilized to ≤ Grade 1 after completion of the steroid taper, then resume: ↓ one dose level. If steroid taper completion is > 28 days: Discontinue further study therapy.	
	3	Hold study therapy and adjust antidiarrheal medication. If event is stabilized to ≤ Grade 1 within 14 days, after completion of the steroid taper, resume: ↓ one dose level. If there is no improvement within 14 days or steroid taper completion is > 28 days: Discontinue further study therapy.	
	4	Discontinue study therapy	
Hepatobiliary Disorders			
Hepatitis/hepatotoxicity (See Sections 8.5.5 , 8.6.2 , and 8.7 .)	3, 4	Discontinue study therapy	

Table 7 continued on next page.

Table 7. Treatment management for study therapy (continued)

CTCAE v4.0 Adverse Event	CTCAE v4.0 Grade	Action to be Taken with Study Therapy	
		Tremelimumab	Durvalumab
Immune System Disorders			
Allergic reaction/ Infusion reaction (See Table 4 and Sections 8.5.1 and 8.5.2 .)	1	The infusion rate of study therapy may be decreased by 50% or temporarily interrupted until resolution of the event. Maintain study dose level.	
	2	The infusion rate of study therapy may be decreased 50% or temporarily interrupted until resolution of the event. Subsequent infusions may be given at 50% of the initial infusion rate. Once event is stabilized to ≤ Grade 1, after completion of the steroid taper, resume: ↓ one dose level. If steroid taper completion is > 28 days: Discontinue further study therapy.	
	3,4	Discontinue study therapy	
Investigations			
Immune-mediated hepatitis as indicated by: 
 • Alanine transferase (ALT) increased • Alkaline phosphatase increased • Aspartate aminotransferase (AST) increased • Blood bilirubin increased Note: Permanently discontinue study therapy for any case meeting Hy's Law criteria. (See Sections 8.5.5 , 8.6.2 , and 8.7 [Hy's Law].)	1	Monitor LFTs; Maintain study dose level.	

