	2	Note: For patients with metastatic liver disease who enter the study with Grade 2 transaminases: Maintain dose and continue study therapy without holding. Otherwise: Hold study therapy. Once elevations have resolved to ≤ Grade 1 and, 
 • No systemic steroid therapy has been initiated then resume: Maintain dose level • Systemic steroid therapy has been initiated – after completion of the steroid taper, resume: ↓ one dose level or discontinue. • If steroid taper completion is > 28 days: Discontinue further study therapy. 	

Table 7 continued on next page.

Table 7. Treatment management for study therapy (continued)

CTCAE v4.0 Adverse Event	CTCAE v4.0 Grade	Action to be Taken with Study Therapy	
		Tremelimumab	Durvalumab
Investigations (continued)			
Immune-mediated hepatitis as indicated by: 
 • Alanine transferase (ALT) increased • Alkaline phosphatase increased • Aspartate aminotransferase (AST) increased • Blood bilirubin increased Note: Permanently discontinue study therapy for any case meeting Hy's Law criteria. (See Sections 8.5.5, 8.6.2, and 8.7 [Hy's Law].)	3	Elevations in transaminases $\leq 8 \times$ ULN and bilirubin $\leq 5 \times$ ULN: Hold study therapy; if elevations resolve to \leq Grade 1 or base line within 14 days , and if 
 • no systemic steroid therapy has been initiated: then resume: Maintain dose or \downarrow one dose level. • systemic steroid therapy has been initiated – after completion of the steroid taper, resume: \downarrow one dose level or discontinue. • If steroid taper completion is > 28 days: discontinue. Note: If elevations do not downgrade to \leq Grade 1 within 14 days OR for elevations in transaminases $> 8 \times$ ULN or bilirubin $> 5 \times$ ULN: Discontinue further study therapy. Discontinue study therapy for any case meeting Hy's law criteria and in the absence of any alternative cause. 	
	4	Discontinue study therapy	
Creatinine increased (Nephritis) (See Sections 8.5.1 and 8.5.6.)	1	Maintain study dose level	
	2	Hold study therapy until resolved to \leq Grade 1 after completion of the steroid taper, resume: \downarrow one dose level. If steroid taper completion is > 28 days: Discontinue further study therapy.	
	3, 4	Discontinue study therapy	

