 - If still no improvement within 3-5 days despite prednisone 1-2mg/kg/day PO or IV equivalent, consider additional workup and prompt treatment with IV methylprednisolone 2-4 mg/kg/day started.
 - If still no improvement within 3-5 days despite 2-4 mg/kg/day of IV methylprednisolone, promptly start immunosuppressives (mycophenolate mofetil). Discuss with study physician if mycophenolate mofetil is not available.

Infliximab should NOT be used.

 - Once improving, gradually taper steroids (28 days of taper) and consider prophylactic antibiotics, antifungals and anti PJP treatment (refer to current NCCN guidelines for treatment of cancer-related infections [Category 2B recommendation]).
 - Report event to DSSM.

Grade 3 or 4 AST or ALT and/or TB elevation:

.For Grade 3:

- For elevations in transaminases $\leq 8 \times$ ULN, or elevations in bilirubin $\leq 5 \times$ ULN:
 - Hold study therapy dose until resolution to Grade ≤ 1 or baseline.
 - Resume study therapy if elevations downgrade to Grade ≤ 1 or baseline within 14 days and after completion of steroid taper.
 - Permanently discontinue study therapy if the elevations do not downgrade to Grade ≤ 1 or baseline within 14 days.
- For elevations in transaminases $> 8 \times$ ULN or elevations in bilirubin $> 5 \times$ ULN, discontinue study therapy.
- Permanently discontinue study therapy for any case meeting Hy's law criteria (AST and/or ALT $> 3 \times$ ULN + bilirubin $> 2 \times$ ULN without initial findings of cholestasis (i.e., elevated alkaline P04) and in the absence of any alternative cause.

Grade 4

- Discontinue study therapy.

Grade 3 or 4:

- Promptly initiate empiric IV methylprednisolone at 1 to 4 mg/kg/day or equivalent.
- If still no improvement within 3-5 days despite 1 to 4 mg/kg/day methylprednisolone IV or equivalent, promptly start treatment with immunosuppressive therapy (mycophenolate mofetil). Discuss with study physician if mycophenolate mofetil is not available.

Infliximab should NOT be used.

- Obtain a Hepatology consult, abdominal workup, and imaging as appropriate.
- Once improving, gradually taper steroids (28 days of taper) and consider prophylactic antibiotics, antifungals and anti PJP treatment (refer to current NCCN guidelines for treatment of cancer-related infections [Category 2B recommendation]).
- Report event to DSSM.

8.5.6 **Nephritis**

(serum creatinine elevation)

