8.7 Liver dysfunction (Hy's Law)

Hy's Law is based on the observation that pure hepatocellular injury sufficient to cause hyperbilirubinemia is an ominous indicator of the potential for a drug to cause serious liver injury. A diagnosis of potential drug-induced liver injury caused by a study drug can only be determined/inferred by excluding other potential causes of liver injury (e.g., other drugs or viral hepatitis) and by ruling out an obstructive cause for the elevated bilirubin (e.g., alkaline phosphatase should not be substantially elevated) ([FDA 2009](#); [Temple 2006](#)).

8.7.1 *Definition of cases potentially meeting Hy's Law criteria*

Patients who present with the following laboratory abnormalities should be evaluated further to definitively determine the etiology of the abnormal laboratory values:

- *Patients with AST or ALT baseline values within the normal range* who subsequently present with AST or ALT > 3 times the ULN concurrent with a total bilirubin > 2 times the ULN with no evidence of hemolysis and an alkaline phosphatase < 2 times the ULN or not available.
- *Patients with pre-existing AST or ALT baseline values above the normal range* who subsequently present with AST or ALT > 2 times the baseline values and > 3 times the ULN, or ≥ 8 times the ULN (whichever is smaller) concurrent with a total bilirubin of > 2 times the ULN and increased by one ULN over baseline or > 3 times the ULN (whichever is smaller) with no evidence of hemolysis and an alkaline phosphatase < 2 times the ULN or not available.

8.7.2 *Evaluation of potential Hy's Law cases*

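### Table 7's permanent stop for Hy's Law cases gives no definition and cites two sections, 8.5.5 and 8.7, whose criteria are not equivalent

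*Combined protocol and SAP*

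**What the plan says.** **Table 7 (Section 8.4), immune-mediated hepatitis.** The note beside the listed laboratory events reads "Permanently discontinue study therapy for any case meeting Hy's Law criteria". It gives no thresholds and sends the site to Sections "8.5.5, 8.6.2, and 8.7 [Hy's Law"]. The Grade 3 cell of the same entry repeats the stop and adds that there must be no other cause. The note itself lacks that condition.

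**Section 8.5.5, Grade 3 block.** "Permanently discontinue study therapy for any case meeting Hy's law criteria (AST and/or ALT" above 3 × ULN, with bilirubin above 2 × "ULN without initial findings of cholestasis (i.e., elevated alkaline P04) and in the absence of any alternative cause"). Baseline values play no part, and no multiple is given for the alkaline phosphatase.

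**Section 8.7.1.** This section defines potential Hy's Law cases. Sections 8.7.1 and 8.7.2 attach further evaluation and SAE reporting to them, not a stop. The 3 × and 2 × ULN thresholds apply only when baseline AST/ALT was normal. For a raised baseline the enzyme condition is "AST or ALT > 2 times the baseline values and > 3 times the ULN, or ≥ 8 times the ULN (whichever is smaller"). Bilirubin must be above 2 × ULN and up by one ULN from baseline, or above 3 × ULN. In both groups alkaline phosphatase must be below 2 × ULN or unavailable, and there must be no sign of hemolysis.

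**Section 4.1.11.** AST and ALT may be up to 2.5 × ULN at entry, with an exception: "for patients with documented liver metastases, AST and ALT must be" no more than 5 × ULN. Bilirubin may be up to 1.5 × ULN, or up to 3 × ULN with Gilbert's disease or a similar syndrome.

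**The concern.** A permanent stop cannot be undone, so two sites with the same liver tests in front of them should reach the same answer. Here the stop note is undefined, and the two places it cites give different tests. The choice matters because the alternatives are reversible. Outside Hy's Law, Table 7 allows a Grade 2 elevation to be held, or therapy to continue if the patient entered with Grade 2 transaminases and metastatic liver disease. A Grade 3 elevation up to 8 × ULN for transaminases and 5 × ULN for bilirubin may be held and therapy resumed if it resolves within 14 days. Which section a site reads can therefore decide between a temporary and a final action. SAP Section 6.2 also counts adverse events leading to permanent discontinuation, and that count could mix two rules.

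**Working it through.** The plan states no figure on this point, so there is none to reproduce. The check sets the two definitions side by side and applies both to the same tests. All values are multiples of ULN.

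**Step 1. The definitions**

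| Condition | 8.5.5 (stop) | 8.7.1 (potential case) |
|---|---|---|
| AST/ALT, normal baseline | > 3 | > 3 |
| AST/ALT, raised baseline | > 3 | > 2 × baseline and > 3, or ≥ 8, whichever is smaller |
| Bilirubin, normal AST/ALT baseline | > 2 | > 2 |
| Bilirubin, raised AST/ALT baseline | > 2 | > 2 and up by 1, or > 3 |
| Alkaline phosphatase | not elevated, no multiple | < 2 or not available |
| Hemolysis | not mentioned | none |
| Alternative cause | none | to be excluded in the evaluation |

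**Step 2. Enzyme threshold by baseline**

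For a raised baseline b > 1, the 8.7.1 threshold is min(max(2b, 3), 8). The 8.5.5 threshold is 3 for every b.

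| Baseline b | 8.5.5 | 8.7.1 | Gap |
|---|---|---|---|
| up to 1.5 | 3 | 3 | 0 |
| 2 | 3 | 4 | 1 |
| 2.5 | 3 | 5 | 2 |
| 3 | 3 | 6 | 3 |
| 4 | 3 | 8 | 5 |
| 5 | 3 | 8 | 5 |

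Baselines up to 2.5 can enter without liver metastases; higher ones only with them. The gap is therefore largest in patients with liver metastases, but it is already present between 1.5 and 2.5 without them.

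**Step 3. Patient A: enzyme condition**

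Liver metastases, baseline AST 4 and bilirubin 1.0; now AST 4.5, bilirubin 2.5, alkaline phosphatase 0.9. No hemolysis and no alternative cause identified.
- 8.5.5: 4.5 > 3, 2.5 > 2, alkaline phosphatase normal. Met.
- 8.7.1: the threshold is min(max(8, 3), 8) = 8, and 4.5 < 8. Not met. The bilirubin condition is met (2.5 > 2, rise 2.5 − 1.0 = 1.5), so the enzyme condition alone separates the two.

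**Step 4. Patient B: bilirubin condition**

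Baseline AST 2 and bilirubin 1.5, both allowed without liver metastases; now AST 6, bilirubin 2.2, alkaline phosphatase 0.9. No hemolysis and no alternative cause identified.
- 8.5.5: 6 > 3 and 2.2 > 2. Met.
- 8.7.1: the enzyme condition is met (6 > 4). Bilirubin rose by 2.2 − 1.5 = 0.7, less than 1, and 2.2 is not above 3. Not met.

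**Step 5. Patient C: alkaline phosphatase condition**

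Normal baseline; now AST 4, bilirubin 2.5, alkaline phosphatase 1.5. No hemolysis and no alternative cause identified.
- 8.7.1: 4 > 3, 2.5 > 2, 1.5 < 2. Met.
- 8.5.5: depends on what elevated means. If it means above 1 × ULN, or above any cut-off below 1.5, the rule is not met and the two sections disagree in the opposite direction. If the cut-off is 1.5 or higher, both are met and there is no conflict for this patient.

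**Step 6. Within Table 7**

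The Grade 3 cell requires that no other cause be present; the note does not. The 8.5.5 clause stands in the Grade 3 block but is worded for any case, and the Table 7 note covers the whole hepatitis entry, so neither confines the stop to one grade.

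**The case against.** The strongest reply is that Section 8.7.1 is not a stopping rule. It screens for potential cases and orders evaluation and SAE reporting, and such a trigger may properly differ from a stopping criterion. On that view 8.5.5 is the only worded stop, and the mention of 8.7 in Table 7 is just a pointer. It is true that the link to stopping runs only through Table 7. But the note offers both sections as the place to find the criteria. Patient A also cannot be explained as the usual wide screen before a narrower stop: that patient meets the stop without being a potential case.

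Second, the alternative-cause condition in 8.5.5 may spare a patient with liver metastases, since that section names disease progression among the causes to consider. This stands, and is why Patients A and B are stated with no alternative cause identified. It is a matter of judgement case by case, and the Table 7 note leaves it out.

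Third, 8.5.5 sets no alkaline phosphatase limit, and the introduction to 8.7 speaks of substantial elevation, so below 2 × ULN could be read as the missing number. This stands, and Patient C is conditional for that reason.

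Four stronger readings are tempting but not supported:
- A reader might infer that the 24-hour SAE report also depends on which section is opened. Sections 8.7.2, 10.4.2 and 10.4.3 tie Hy's Law reporting to 8.7 alone, and adverse events of special interest of Grade 2 or higher, which include hepatitis and transaminase increases, are expedited anyway.
- A reader might infer that an eligible patient with Gilbert's disease and liver metastases meets the stop before the first dose. Section 8.4 modifies dosing after the first dose, for events at least partly due to study drug, and Gilbert's disease is itself another explanation for the bilirubin.
- A reader might infer a shift in the objective response rate through patients stopped before the first restaging scan. The documents give no frequency from which to estimate one.
- A reader might infer that the conflict falls mainly on patients with liver metastases. That describes where the enzyme gap is largest; the alkaline phosphatase condition applies at any baseline.

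**Conclusion.** The inconsistency is real and should be corrected. Table 7's permanent stop rests on criteria it does not state, and the two sections it cites classify some identical liver tests differently. For a raised baseline the AST/ALT thresholds are 3 against 4, 6 and 8 × ULN at baselines of 2, 3 and 4 to 5 × ULN, all within the entry limits of Section 4.1.11. The bilirubin, alkaline phosphatase and hemolysis conditions differ as well. Disagreement in one direction (8.5.5 met, 8.7.1 not) needs only that no alternative cause is identified. Disagreement in the other direction assumes that elevated alkaline phosphatase in 8.5.5 means above 1 × ULN, or at least a cut-off below the observed value. How many patients would be affected cannot be estimated from the documents.

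**What to change.** The sponsor should reconcile Section 8.5.5, Section 8.7.1 and Table 7. Either of two forms would do:
- One Hy's Law definition, stated once and cross-referenced elsewhere. It should be explicit on AST/ALT and bilirubin raised at baseline, the alkaline phosphatase limit, hemolysis and alternative cause.
- If the stopping and reporting triggers are meant to differ, two separately named definitions, with the Table 7 stop note citing only the stopping one.

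Either way, the Table 7 note and its Grade 3 cell should carry the same alternative-cause wording. Which criterion is clinically right is for the sponsor to decide; no view is given here.

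The cost is a wording change in three places in an amendment. No tests are added: AST, ALT, bilirubin and alkaline phosphatase are already required before entry in Table 1 and during treatment in Table 2.

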8.2 Treatment management for durvalumab and tremelimumab

The study treatment schedule should be maintained. If necessary, the timing of a treatment may be adjusted to 3 days earlier or 3 days later than the scheduled date of treatment. All doses administered or missed must be recorded.

8.2.1 *Treatment decisions when therapy must be held*

- In the event systemic steroid therapy is initiated for toxicity management, study therapy must be held. The steroid taper should be completed within 28 days. Study therapy may then be resumed after completion of the steroid taper on Day 1 of the next scheduled cycle.
- Note: Should the steroid taper require a slower rate for completion (i.e., > 28 days), further study therapy doses must be discontinued.
- See [Table 7](#) for treatment management.

8.2.2 *Treatment decisions when therapy must be discontinued*

Treatment must be discontinued if:

- If either durvalumab or tremelimumab must be held for > 28 days of continuous delay for other than steroid taper (e.g., toxicity).
- Consent is withdrawn or patient is lost to follow-up. If consent is withdrawn, the patient will not receive any further investigational product or further study observation.
- An adverse event occurs that, in the opinion of the investigator or sponsor, contradicts further dosing.
- The patient becomes pregnant or intends to conceive a child while actively on study.
- Grade 3 or greater infusion reaction occurs.
- Bullous rash.
- Diagnosis of Guillain-Barre and/or Myasthenia Gravis.
- Initiation of alternate cancer therapy including another investigational agent.
- If tumor progression occurs during study therapy, durvalumab must be discontinued. See [Section 11.0](#).

See [Table 7](#) for additional treatment management requirements. Patients who prematurely discontinue study therapy should complete assessments on [Table 2](#).

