8.4 Dose modification and management of toxicities

All toxicities will be graded according to CTCAE version 4.0. Following the first dose of durvalumab and tremelimumab, subsequent administration of durvalumab and tremelimumab can be modified based on toxicities observed as described in [Sections 8.5, 8.6, and 8.7](#). For adverse events (AEs) that are considered at least partly due to administration of durvalumab or tremelimumab, the following general guidance may be applied:

- Treat each of the toxicities with maximum supportive care (including holding the study therapy suspected of causing the toxicity where required).
- All dose modifications should be documented with clear reasoning and documentation of the approach taken.
- In addition to the criteria for permanent discontinuation of study therapy based on toxicity grade, permanently discontinue study therapy for the conditions outlined in [Section 8.2.2](#).

Table 7. Treatment management for study therapy (durvalumab and tremelimumab)

CTCAE v4.0 Adverse Event	CTCAE v4.0 Grade	Action to be Taken with Study Therapy	
		Tremelimumab	Durvalumab
Cardiac Disorders			
Myocarditis (See Sections 8.5.1 and 8.5.12)	1	For suspected myocarditis: Hold study therapy until full diagnostic work up. Initiate steroid therapy and appropriate management. If study therapy is held, resume after complete resolution to Grade 0 after completion of the steroid taper, resume at the next scheduled dose.	
	2	Hold study therapy dose until resolution to Grade 0. If toxicity rapidly improves to Grade 0, then: The decision to reinstitute study therapy will be based upon treating physician’s clinical judgment and after completion of steroid taper. If toxicity does not rapidly improve, permanently: Discontinue study therapy.	
	3-4	Discontinue study therapy	
Endocrine disorders			
Endocrinopathy (e.g., hyperthyroidism, hypothyroidism, Type 1 diabetes mellitus, hypophysitis, hypopituitarism, and adrenal insufficiency; exocrine event of amylase/lipase increased also included in this section) (See Sections 8.5.1 and 8.5.8).	1	No dose modifications.	

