	3	Hold study therapy dose until resolution to Grade \leq 1. Permanently discontinue study therapy if it does not resolve to Grade \leq 1 within 28 days or if there are signs of respiratory insufficiency or autonomic instability.	
	4	Discontinue study therapy	
Respiratory, thoracic, and mediastinal disorders			
Pneumonitis/pulmonary infiltrates/other pulmonary events 
 Dyspnea Hypoxia Pneumonitis ILD Pulmonary fibrosis (See Sections 8.5.1 , 8.5.3 , and 8.6.1.)	Hold study treatment until pneumonitis is evaluated.		
	1	Maintain study therapy schedule without delay.	
	2	Hold study therapy. At physician's discretion, once event is stabilized to \leq Grade 1 after completion of the steroid taper, then resume: \downarrow one dose level. If steroid taper completion is $>$ 28 days: discontinue further study therapy.	
3,4	Discontinue study therapy		

Table 7 continued on next page.

Table 7. Treatment management for study therapy (continued)

CTCAE v4.0 Adverse Event	CTCAE v4.0 Grade	Action to be Taken with Study Therapy	
		Tremelimumab	Durvalumab
Skin and subcutaneous tissue disorders			
Rash/dermatitis (e.g., acneiform, maculo-papular) (See Sections 8.5.1 and 8.5.7.)	1	Maintain dose level	
	2	Hold study therapy until resolution to ≤ Grade 1 or baseline and if 
 no systemic steroid therapy has been initiated—resume: Maintain dose level or ↓ one dose level. systemic steroid therapy has been initiated –after completion of the steroid taper: Maintain dose level or ↓ one dose level. If steroid taper completion is > 28 days: discontinue further study therapy .	
	3	Hold study therapy until resolution to ≤ Grade 1 or baseline and if 
 no systemic steroid therapy has been initiated—resume: ↓ one dose level or discontinue. systemic steroid therapy has been initiated –after completion of the steroid taper: ↓ one dose level or discontinue. If steroid taper completion is > 28 days: Discontinue further study therapy .	
	4	Discontinue study therapy	
Rash (e.g., bullous skin formations) (See Section 8.5.7)	All Grades	Discontinue study therapy	
AEs of Non-Immune Mediated Reactions			
AEs of non-immune mediated reaction requiring dose modification per investigator (e.g., Section 8.5.1)	1	Maintain dose	

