Patients should be evaluated to rule out any alternative etiology (e.g., disease progression, infections, metabolic syndromes and medications, etc.). It should be noted that the diagnosis of immune-mediated peripheral neuromotor syndromes can be particularly challenging in patients with underlying cancer, due to the multiple potential confounding effects of cancer (and its treatments) throughout the neuraxis. Given the importance of prompt and accurate diagnosis, it is essential to have a low threshold to obtain a neurological consult. **If Myasthenia Gravis or Guillain-Barre is confirmed, discontinue study therapy.**

Neurophysiologic diagnostic testing (e.g., electromyogram and nerve conduction investigations, and “repetitive stimulation” if myasthenia is suspected) are routinely indicated upon suspicion of such conditions and may be best facilitated by means of a neurology consultation.

It is important to consider that the use of steroids as the primary treatment of Guillain-Barre is not typically considered effective. Patients requiring treatment should be started with IV IG and followed by plasmapheresis if not responsive to IV IG. See [Table 7](#).

- *Grade 1:*
 - Hold study therapy.
 - Contact DSSM.
 - Care should be taken to monitor patients for sentinel symptoms of a potential decompensation as described above.
 - Obtain a Neurology consult unless the symptoms are very minor and stable. If Myasthenia Gravis or Guillain-Barre is confirmed, discontinue study therapy and report event to DSSM.
- *Grades 2, 3 and 4:*
 - Hold study therapy during work-up of symptoms. If Myasthenia Gravis or Guillain-Barre is confirmed, discontinue study therapy. If negative hold therapy until \leq Grade 1 and prednisone dose is \leq 10 mg/day or the equivalent.
 - Report event to DSSM.
 - Care should be taken to monitor patients for sentinel symptoms of a potential decompensation as described above.
 - Obtain a Neurology consult.
 - Sensory neuropathy/neuropathic pain may be managed by appropriate medications (e.g., gabapentin, duloxetine, etc.).

MYASTHENIA GRAVIS

- Steroids may be successfully used to treat Myasthenia Gravis. Important to

consider that steroid therapy (especially with high doses) may result in transient worsening of myasthenia and should typically be administered in a monitored setting under supervision of a consulting neurologist.

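### For Grade 2-3 peripheral neuromotor events with a negative work-up, the hold condition in protocol 8.5.10 (prednisone 10 mg/day or less) is looser than the mandatory taper rule in 8.2.1

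*Combined protocol and SAP*

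**What the plan says.** Section 8.5.10 covers peripheral neuromotor syndromes. Its bullet for Grades 2, 3 and 4 has therapy held during work-up and then reads "If Myasthenia Gravis or Guillain-Barre is confirmed, discontinue study therapy. If negative hold therapy until" at or below "Grade 1 and prednisone dose is" at or below "10 mg/day or the equivalent". It mentions neither completion of the taper nor a limit on taper length.

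Section 8.2.1 applies whenever systemic steroids are started to manage toxicity. Therapy must then be held. On restarting it says "Study therapy may then be resumed after completion of the steroid taper on Day 1 of the next scheduled cycle". Its Note adds that if the taper needs more than 28 days, "further study therapy doses must be discontinued".

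Three other places bear on how a site would read these two texts:

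- Section 8.4 says "subsequent administration of durvalumab and tremelimumab can be modified based on toxicities observed as described in" Sections 8.5, 8.6 and 8.7.
- The introduction to 8.5 calls its guidance recommended and refers to Table 7 for study-drug dosing.
- The Table 7 row for peripheral neuromotor syndrome cites 8.5.10. At Grades 2 and 3 it requires a permanent stop if the event does not settle to Grade 1 or less "within 28 days or if there are signs of respiratory insufficiency or autonomic instability". That 28-day clock runs on the event, not on the taper, and the row has no steroid condition.

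The separate Table 7 row for Neurotoxicity, which excludes Guillain-Barre and myasthenia gravis and cites 8.5.9, does require a finished taper at Grades 2-3 and a stop beyond 28 days.

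**The concern.** The bullet's prednisone threshold presupposes a patient on steroids, which is exactly the situation that 8.2.1 regulates. The two texts end the hold at different points. A site that takes the bullet as its restart rule could give a checkpoint inhibitor after neurologic toxicity while immunosuppression is still being withdrawn. With a taper over 28 days, it could continue treatment that 8.2.1 ends. Section 8.5.1 foresees such tapers when symptoms recur during steroid reduction, and 8.5.10 itself warns that these syndromes can decompensate suddenly.

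The wording does not look like a deliberate exception. Where the protocol wants a 10 mg/day allowance for retreatment, it writes one out with conditions, for endocrinopathies needing prolonged steroid replacement (Table 7 and 8.5.8). The 10 mg/day figure in 4.2.10 is an entry limit, not a restart rule.

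**Working it through.** No figure in the plan needs reproducing. The check is to apply both texts to the same patient.

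| Patient after a negative work-up (Grade 2-3 event) | 8.5.10 bullet | 8.2.1 |
|---|---|---|
| Grade 1 or less, no systemic steroid given | hold ends | not triggered |
| Still Grade 2 or more, on steroids | hold | hold (stop if taper over 28 days) |
| Grade 1 or less, prednisone above 10 mg/day | hold | hold (stop if taper over 28 days) |
| Grade 1 or less, prednisone 10 mg/day or less, taper will end within 28 days | hold may end | hold until taper is complete |
| Grade 1 or less, prednisone 10 mg/day or less, taper over 28 days | hold may end | permanent stop |

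The bullet allows a dose that 8.2.1 forbids in the last two rows. The fourth is a matter of timing; the fifth decides whether the patient is treated again. Grade 4 is in the bullet's heading, but Table 7 and the later Grade 4 block of 8.5.10 make it a stop in any case.

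**Illustration for tapers of 28 days or less.** The documents give no taper schedule, so assume a straight-line taper to zero over T days from D mg/day. Prednisone then reaches 10 mg/day T × 10 / D days before the taper ends. Section 8.5.1 gives 1-2 mg/kg/day and 2.5.1 a typical weight of 75 kg, so D = 75 to 150 mg/day.

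- T = 28: 28 × 10 / 75 = 3.7 days; 28 × 10 / 150 = 1.9 days.
- The cycle dosed differs only if a scheduled Day 1 falls in that gap. Assume steroid starts are spread evenly over a 28-day cycle, with the 3-day scheduling window applied alike under both rules. The share is then gap / 28: 3.73 / 28 = 13.3% and 1.87 / 28 = 6.7%.
- Over the 40-120 kg range in 2.5.1: 28 × 10 / 40 = 7.0 days (25%) down to 28 × 10 / 240 = 1.2 days (4.2%).
- T = 14 at 75 kg: 14 × 10 / 75 = 1.9 days (6.7%) and 14 × 10 / 150 = 0.9 days (3.3%).

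These shares assume that Grade 1 has already been reached when prednisone falls to 10 mg/day. Later resolution shrinks the gap; a taper that lingers at low doses would widen it.

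**Ceiling for tapers over 28 days.** With 24 planned durvalumab doses and 4 tremelimumab doses, an event after the Cycle 1 dose leaves at most 24 − 1 = 23 and 4 − 1 = 3. After Cycle 4 it leaves 24 − 4 = 20 and 4 − 4 = 0. Every dose missed during the hold lowers these counts.

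**The case against.** The best answer is that the two texts can be obeyed together. The bullet sets a minimum hold. It does not order a restart or waive 8.2.1, and a site that follows the stricter text complies with both. Section 8.2.1 is mandatory and 8.5 is only recommended. Once both named syndromes are excluded, the Table 7 Neurotoxicity row is a natural home for the patient and carries the right rule. All of this stands, so a reader should not infer that the protocol authorises re-dosing during a taper or leaves the case without a governing rule.

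Nor should a reader infer that long tapers escape because the 28-day hold limit in 8.2.2 is written for delays "for other than steroid taper (e.g., toxicity". The Note in 8.2.1, directly above, deals with tapers over 28 days; 8.2.2 covers the remaining delays.

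Safeguards also count: 8.5.10 requires a neurology consult and a report to DSSM, immune-mediated events of Grade 2 or more need expedited reporting within 24 hours (10.4.2, 10.7.2), and 14.3 provides a weekly investigator call and monthly medical review. Recurrent symptoms may also trigger the separate 28-day stop on resolution of the event.

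What these points do not do is reconcile the bullet with 8.2.1. The neuromotor row of Table 7 cites 8.5.10, where the only steroid condition for ending the hold is the looser one.

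**Conclusion.** The inconsistency is real and worth correcting, but it is small. Section 8.2.1 governs; the fault is that an event-specific bullet says something looser and the Table 7 row citing that section is silent on steroids. The affected patient has a Grade 2-3 neuromotor event, both named syndromes excluded, systemic steroids given, and a site that reads the bullet as sufficient. The documents give no frequency for this, and the trial plans only 12 to 21 evaluable patients.

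For tapers of 28 days or less the difference is timing, and under the assumptions above it usually changes no dose. For longer tapers it is a permanent stop against possible continuation. A reader might take the 23 durvalumab and 3 tremelimumab doses as the expected effect; they are a ceiling, because a relapse followed by a slow taper after Cycle 1 would usually outlast the Cycle 2 date. The percentages depend on a taper shape that the documents do not specify and are illustrative only. Nothing here alters the Simon stage sizes, cut-offs or error rates.

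**What to change.** In the 8.5.10 bullet, limit the hold-until sentence to Grades 2-3 and replace the 10 mg/day condition with: *Grade 1 or less and, if systemic steroids were started, completion of the steroid taper; discontinue if the taper exceeds 28 days (8.2.1)*. Add the same condition to the Grade 2 and Grade 3 entries of the Table 7 peripheral neuromotor row.

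The cost is one bullet and two table entries, using a taper rule that other Table 7 rows already carry (for example diarrhea, nephritis, neurotoxicity and pneumonitis). Design, sample size and analysis do not change. The one downside is that some patients will restart a cycle later than the bullet now suggests.
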